#### 9.1.4 Pooling

Summary statistics will be calculated by treatment (and time point, if applicable).

#### 9.1.5 Unscheduled Measurements

Unscheduled measurements will be included in the listings. With the exception of unscheduled measurements used for baseline, unscheduled measurements will be excluded from the descriptive statistics and statistical analysis.

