#### 9.1.3 Descriptive Statistics

Unless otherwise indicated, continuous variables will be summarized with the following descriptive statistics: n (number of observations), (arithmetic) mean, SD, minimum (min) value, median, and maximum (max) value. For PK parameters the geometric mean (except for  $t_{max}$ ) and the coefficient of variation (CV%) will also be presented.

Categorical data will be summarized with frequencies and percentages. Percentages by categories will be based on the number of subjects exposed within a treatment.

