### 17.1.5 Electrocardiograms

ECG parameters will be listed and descriptive statistics of original values and change from baseline will be provided to summarize ECG parameters by treatment and scheduled time. At some time points triplicate 12-lead ECGs will be recorded. The average of these triplicate values will be used in the calculation of descriptive statistics and change from baseline, and the average of the triplicate values at pre-dose will be used as baseline. The individual triplicate values will be listed.

A frequency table of QTc (Bazett and Fridericia) values will be presented by treatment and scheduled time. The number of incidences (number of subjects) and percentage of subjects will be presented. The following categories will be used:

- < 450 ms
- $\geq$  450 - 480 ms
- $\geq$  480 - 500 ms
- $\geq$  500 ms

A frequency table of QTc (Bazett and Fridericia) change from baseline values will be presented by treatment and scheduled time. The number of incidences (number of subjects) and percentage of subjects will be presented. The following categories will be used:

- < 30 ms
- $\geq$  30 - 60 ms
- $\geq$  60 ms

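### The two QTc category tables leave out post-dose unscheduled ECGs and give subject counts only per scheduled time, so the number of subjects ever reaching a category on a treatment is not shown

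*SAP*

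**What the plan says.** SAP 17.1.5 (Electrocardiograms) sets the layout of both tables:

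- Absolute values: "A frequency table of QTc (Bazett and Fridericia) values will be presented by treatment and scheduled time". The category limits are 450, 480 and 500 ms.
- Change from baseline: "A frequency table of QTc (Bazett and Fridericia) change from baseline values will be presented by treatment and scheduled time". The category limits are 30 and 60 ms.
- Cell content in both: "The number of incidences (number of subjects) and percentage of subjects will be presented".

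SAP 9.1.5 (Unscheduled Measurements) first states "Unscheduled measurements will be included in the listings". It then sets the rule for summaries: "With the exception of unscheduled measurements used for baseline", "unscheduled measurements will be excluded from the descriptive statistics and statistical analysis".

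SAP 9.1.3 (Descriptive Statistics) covers frequency tables under that same heading: "Categorical data will be summarized with frequencies and percentages". It also fixes the denominator: "Percentages by categories will be based on the number of subjects exposed within a treatment".

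Appendix 5 lists the two tables as 15.3.4.3 and 15.3.4.4, with no further QTc category output. Appendix 6 lists the ECG results as Listing 16.2.8.2.

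**The concern.** Leaving out unscheduled values makes sense for means and SDs at planned times, where an extra reading belongs to no row. A threshold table has a different purpose. Its reader wants to know whether anyone crossed a limit on a treatment, and how many subjects did. Under these rules a top category can read zero throughout while the listing holds a value in it. Even for scheduled ECGs alone, counts by time do not add up to a count of subjects.

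Safety of OZ439 alone and with cobicistat is a secondary objective (SAP 5.2), and ECG is a named safety endpoint in both parts (SAP 5.2.1). The Part 2 sample size assumes that cobicistat doubles OZ439 exposure (SAP 6.1), so Treatments C and D are where a reader would look for a QTc difference related to exposure.

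**Working it through.** No figure in the SAP is at issue, so there is none to reproduce. The check has two steps.

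**Step 1: which ECGs can enter the tables.**

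- 9.1.3 treats category frequencies as descriptive statistics.
- 9.1.5 removes unscheduled values from descriptive statistics, except those used for baseline.
- 17.1.5 breaks the tables down by scheduled time and provides no row for other readings.

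So a post-dose unscheduled ECG cannot enter Table 15.3.4.3 or 15.3.4.4. Table 15.3.4.2 (ECG summary) does not fill the gap: its maximum is also a descriptive statistic at a scheduled time. For laboratory data, 17.1.3 adds a summary listing of values outside the reference range (Table 15.3.3.1). ECG has no equivalent, so Listing 16.2.8.2 is the only place left.

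The effect for one subject above a limit only on an unscheduled ECG is:

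- Part 2: the table shows 0/18, while the any-time count is 1/18 = 5.6%.
- Part 1: the table shows 0/8, while the any-time count is 1/8 = 12.5%.

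**Step 2: what by-time counts say about subjects.**

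Let n be the subjects exposed to a treatment, K the number of post-dose scheduled ECG times, and c_k the number of subjects at or above a limit at time k. The number N of distinct subjects ever at or above it satisfies

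max(c_k) ≤ N ≤ min(n, Σc_k).

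Inputs: n = 18 (Part 2) and n = 8 (Part 1), from SAP 6.0. K is assumed to be 4 to 8, because the column alignment of the schedule in the appendices could not be read reliably. The c_k are assumed, since the SAP gives no QTc rates. With one subject in every row (c_k = 1), the bounds are 1 ≤ N ≤ min(n, K):

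| n | Each row shows | K | Smallest N | Largest N |
|---|---|---|---|---|
| 18 | 1/18 = 5.6% | 4 | 1/18 = 5.6% | 4/18 = 22.2% |
| 18 | 5.6% | 7 | 5.6% | 7/18 = 38.9% |
| 18 | 5.6% | 8 | 5.6% | 8/18 = 44.4% |
| 8 | 1/8 = 12.5% | 4 | 1/8 = 12.5% | 4/8 = 50.0% |
| 8 | 12.5% | 7 | 12.5% | 7/8 = 87.5% |
| 8 | 12.5% | 8 | 12.5% | 8/8 = 100% |

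The same table can come from one subject who is prolonged throughout or from a different subject at each time. The choice of K changes the width of the range but not this conclusion.

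**The case against.** The strongest reply is that 9.1.5 and 17.1.5 are clear, agree with each other and contain no error. The study is exploratory, no QTc hypothesis is tested, and SAP 3.0 allows unplanned analyses to be added and identified in the CSR. The largest scheduled QTc and the largest change at each time appear as maxima in the ECG summary. With 26 planned subjects (8 + 18), anyone can count those affected from the listing. All of this is true, and it is why the point is an improvement to the summary and not a correction of a mistake. It does not change the fact that the tables built for thresholds leave the subject count to be done by hand.

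A second reply concerns the remedy. Appendix 3 gives Treatment D extra visits on Days 10, 12 and 14. If the ECG marks are aligned with the triplicates required at 2 and 4 hours, the schedule appears to place an ECG at 216 hours, which is Day 10 ((10 − 1) × 24 = 216). A worst-value row over the whole period would then give D more chances than C to cross a limit. In addition, triplicates are required only at pre-dose, 2 and 4 hours, so a maximum over single readings set against a triplicate-averaged baseline tends to run high. Both points stand, and the remedy has to deal with them.

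A reader might also infer more than the SAP supports:

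- That affected subjects are never counted. They are, per treatment and scheduled time; only the count across times is absent.
- That confirmed prolongations are lost. If a repeat confirms a prolonged scheduled ECG, the scheduled value is still counted.
- That every unscheduled ECG is discarded. Values used for baseline are exempt, and all values are listed.
- That the rule removes the most abnormal readings. The SAP gives no reason for taking an unscheduled ECG, and poor tracing quality is as possible as symptoms or an abnormal reading.

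**Conclusion.** The point holds in a limited form, as a cheap improvement. As written, the QTc category tables cannot show a prolongation first seen, or in a higher category, on a post-dose unscheduled ECG. They also do not give the number of distinct subjects ever reaching a category on a treatment. The first part follows from 9.1.3, 9.1.5 and 17.1.5 read together, and the second from the table layout and the output list in Appendix 5.

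The size cannot be stated. The range of 5.6% to 38.9% for one subject in each of 7 rows is a counting bound under assumed counts and an assumed number of rows. It is not an expected result. The documents do not support a claim that the tables will understate risk by any particular amount. The primary analyses are not affected.

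**What to change.** In 17.1.5, keep the by-time rows and add one row per treatment to both QTc tables. For each correction (Bazett and Fridericia) it would show each subject's worst post-dose result in the period: the highest value in Table 15.3.4.3 and the largest increase in Table 15.3.4.4. Use scheduled and unscheduled ECGs, with triplicates averaged first. In 9.1.5, exempt this row from the exclusion of unscheduled values.

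For the comparison of C with D, base the row on the post-dose window common to all Part 2 treatments. Under Appendix 3, footnote 1, the last ambulatory visit shared by every period is Day 8 (168 hours). Show any later Treatment D values separately or in a footnote.

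The cost is minor programming on data that are already collected and listed. There are two downsides to state in a footnote: subjects with more repeat ECGs have more chances to be counted, and a maximum over single readings against a triplicate-averaged baseline tends to run high.

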### 9.2 Analysis Data Definitions

#### 9.2.1 Baseline Definition

Unless otherwise stated, baseline for post-dose evaluations within each period is defined as the last observation recorded before the first study drug administration in each period. The last observation can be an unscheduled / repeated measurement.

#### 9.2.2 Treatment/Subject Grouping Definition

Throughout this SAP treatment refers to Treatment A, B, C, and D (see Section 6.0).

#### 9.2.3 Other Definitions

Variable	Data Type	Definition/Calculation
Change from Baseline	All	Post-dose Observation minus Baseline Observation
Study Day (Prior to Dose)	All	Date of Measurement minus first Dose Date for each period
Study Day (Post-Dose)	All	Date of Measurement minus first Dose Date +1 for each period
TEAE	Adverse Events	AE is a TEAE if the AE Date/Time is greater than the first OZ439 or cobicistat Dose Date/Time
Time post dose	PK	Time relative to drug administration. For the iv treatment time post dose will be relative to the iv drug administration (3 hours after the oral administration)

### 9.2.4 Critical Data

As the primary objective of this study is to determine bioavailability and to characterize the PK, the datasets considered critical are Pharmacokinetic Parameters Analysis Dataset (ADPP) and Subject Level Analysis Dataset (ADSL).

The analysis datasets that will be created are ADSL, ADAE, ADLB, ADVS, ADEG, ADPC and ADPP. The analysis datasets will be generated in accordance with Clinical Data Interchange Standard Consortium (CDISC) Analysis Data Model (ADaM) Version 2.1 (ADaM Implementation Guide v1.1). ADaM compliant datasets will be delivered to the Sponsor, including a define.xml (not including analysis results metadata).

### 9.2.5 QC

The analysis datasets and the TFLs will be QC'd according to the general PRA EDS QC plan.

## 9.3 Software

The statistical analysis and reporting will be done using SAS® for Windows™ Version 9.4 or higher (SAS Institute, Inc.).

PK parameter calculations will be done using Phoenix® WinNonlin® Version 6.3 or higher (Pharsight, Inc.).

## 9.4 Statistical Methods

### 9.4.1 Statistical Outlier Determination

No statistical outlier analysis is planned.

### 9.4.2 Predetermined Covariates and Prognostic Factors

There are no predetermined covariates or prognostic factors.

## 9.5 TFL Layout

Report layout will be according to the PRA EDS – ICH E3 compliant – CSR Template. The layout of TFLs will be according to the PRA EDS standards.

No table shells will be provided. The TFLs will be provided in Adobe PDF format (in A4 Format).

Format:

- Data in listings will be sorted by subject number, period and time point.

- Data in tables will be sorted by treatment and time point.
- Column titles will be in title case letters.
- All tables and listings will be in landscape format. For figures, the portrait format may be used as well.
- The treatment labels A, B, C, and D will be used in the TFLs, with footnotes explaining the abbreviations.

## 10.0 Analysis Sets

Analyses	Randomized Set	Safety Set	Pharmacokinetic Set
Disposition Summaries	✓		
Safety Assessments		✓	
Baseline Characteristics		✓	
Primary Analysis			✓
PK Concentrations		✓	
PK Parameters			✓

### 10.1 Randomized

The randomized set will consist of subjects who are assigned a randomization number in the study. This set will be used for disposition summaries.

### 10.2 Safety

The safety set will consist of subjects who receive at least 1 dose of OZ439. This set will be used for the safety data summaries, baseline characteristic summaries, and PK concentration summaries.

### 10.3 Pharmacokinetic

The PK set will consist of all subjects who receive at least 1 dose of OZ439 and provided sufficient bioanalytical assessment results to calculate reliable estimates of at least one of the primary endpoints PK parameters or secondary endpoint parameters. This set will be used for descriptive statistics of PK parameters.

### 10.4 Pharmacokinetic Summary

The PK summary set will consist of all subjects who are considered evaluable for the primary statistical analysis, defined as follows:

For Part 2, a subject will be considered evaluable for the primary statistical analysis if they have sufficient PK data to estimate the primary endpoints  $C_{max}$  and  $AUC_{0-inf}$  for the 3 treatments.

For Part 1, a subject will be considered evaluable for the primary statistical analysis (bioavailability) if they have sufficient PK data to estimate the primary endpoint  $F_{po}$ .

This set will be used for the statistical analysis of the treatment comparisons defined in Section 16.3.1.

## 11.0 Subject Disposition

A listing containing the information for each subject with regard to completing the study and study withdrawal will be presented.

The number and percentage of subjects randomized, dosed, and members of each analysis set will be presented. The number and percentage of subjects who withdrew from the study prematurely and a breakdown of the corresponding reasons for withdrawal will also be presented.

A listing containing study dates by subject will be presented, containing the following dates: informed consent, screening, dose administration in each period, follow-up and last assessment.

## 12.0 Protocol Deviations and Violations

Protocol deviations/violations will be included in the CSR.

## 13.0 Demographic and Baseline Characteristics

### 13.1 Demographics

Individual demographic data will be listed.

Subject demographics will be summarized descriptively for all subjects by study part. The summary will include the subjects' age at informed consent (in years), gender, race, ethnicity, weight (in kg), height (in cm), and body mass index (BMI) (in kg/m^2). Demographics will be summarized for the safety and PK sets.

### 13.2 Medical History

Medical history will be listed.

### 13.3 Other Baseline Characteristics

The results of drug and alcohol screen at screening and admission will be listed.

The results of serology at screening will be listed.

The results of pregnancy tests at screening and admission will be listed (females only).

The results of hormone tests (follicle stimulating hormone [FSH]) at screening for females only will be listed.

## 14.0 Prior/Concomitant Medications

Concomitant medication will be listed. Medications with an end date prior to the first dose of study drug will be considered prior medications and will be listed separately. If a partial date allows a medication to be considered concomitant it will be categorized as such.

## 15.0 Treatment Compliance and Exposure

Study drug administration data will be listed by subject.

## 16.0 Pharmacokinetic Analyses

The plasma samples for OZ439 and Cobicistat will be analyzed by Swiss Bioquant AG and concentration data will be transferred to PRA.

The plasma samples for [C]-OZ439 will be analyzed by transferred Xceleron Inc and concentration data will be transferred to PRA.

## 16.1 Pharmacokinetic Variables

- Plasma concentrations of OZ439 (Part 1 and Part 2)
- Plasma concentrations of [C]-OZ439 (Part 1)
- Plasma concentrations of cobicistat (part 2)
- Plasma concentrations of total radioactivity (Part 1)
- PK parameters for OZ439 in plasma (Part 1 and Part 2)
- PK parameters for [C]-OZ439 in plasma (Part 1)
- PK parameters for total radioactivity in plasma (Part 1)
- PK parameters for cobicistat (Part 2)

Parameter	Description	SAS Programming Notes	Part 1 OZ439 iv/oral	Part 2 OZ439/cobicistat
C max	Maximum plasma concentration. Observed peak analyte concentration obtained directly from the experimental data without interpolation, expressed in concentration units	C max from WNL	iv and oral	OZ439 and cobicistat
C 168h	Observed plasma concentration at 168 hours post-dose		oral	OZ439
T max	Time to maximum plasma concentration. First observed time to reach peak analyte concentration obtained directly from the experimental data without interpolation, expressed in time units.	T max from WNL	iv and oral	OZ439 and cobicistat
AUCs	Calculated using linear up / log down, expressed in units of concentration x time.			
AUC 0-t	Area under the concentration-time curve (time 0 to time of last quantifiable concentration).	AUC last from WNL	iv and oral	OZ439 and cobicistat
AUC 0-inf	Area under the plasma concentration-time curve (time 0 to infinity). Percent extrapolation less than or equal to 20% is required to retain AUC inf .	AUC INF_obs from WNL If AUC_%Extrap_obs >20% then parameter is flagged	iv and oral	OZ439 and cobicistat
%AUC extra	Percentage of estimated part for the calculation of AUC. $\%AUC_{extra} = ((AUC_{0-inf} - AUC_{0-t}) / AUC_{0-inf}) * 100\%$ .	AUC_%Extrap_obs from WNL	iv and oral	OZ439 and cobicistat
AUC 0-168	Area under the serum concentration-time curve from time 0 to 168 hours post-dose.	AUC 0-168 from WNL where partial time = 168	oral	OZ439
λ z	Terminal phase rate constant	Lambda z from WNL	iv and oral	OZ439 and

Parameter	Description	SAS Programming Notes	Part 1 OZ439 iv/ oral	Part 2 OZ439/ cobicistat
	calculated by linear regression of the terminal log-linear portion of the concentration vs. time curve. Linear regression of at least three is required (regression of two points will be flagged).	If adjusted Rsq $\leq$ .80 then parameter is flagged		cobicistat
t 1/2	Terminal phase half-life expressed in time units.	HL_Lambda_z from WNL If adjusted Rsq $\leq$ .80 then parameter is flagged	iv and oral	OZ439 and cobicistat
CL/F	Apparent oral clearance, calculated	Cl_F_obs from WNL	oral	cobicistat
CL	Clearance, calculated as dose/AUC 0-inf	Cl_obs from WNL	iv	OZ439
V d	Volume of distribution at terminal phase, calculated as CL/ $\lambda_z$	Vz_F_obs from WNL	iv	OZ439
F po	Absolute bioavailability, calculated as: $F = (AUC_{\text{oral}} * D_{\text{iv}}) / (AUC_{\text{iv}} * D_{\text{oral}})$ , where AUC oral is the AUC 0-inf of OZ439 and AUC iv is the AUC 0-inf of [  C]-OZ439; D oral is the oral dose and D iv is the iv microdose			OZ439

## 16.2 Pharmacokinetic Concentrations

Plasma concentrations for total radioactivity, [C]-OZ439, OZ439 or cobicistat below the quantifiable limit (BQL) will be set to ½ LLOQ in the computation of mean concentration values. Descriptive statistics (number of subjects, arithmetic mean, geometric mean, SD, CV%, median, minimum, and maximum) will be used to summarize the plasma concentrations by treatment at each scheduled time point. If over ½ the subjects in a given cell have values BQL then the descriptive statistics will not be presented except for the minimum and maximum and the mean will be displayed as BQL.

Linear and semi-logarithmic plots of the geometric mean total radioactivity, OZ439 and cobicistat plasma concentration by scheduled sampling time will be provided by treatment. These plots will show time in hours. The plots will match the summary table results and will not have an observation at a given time point if more than half of the subjects have values BQL. The following mean plots will be provided:

- Geometric mean oral OZ439 concentration, iv total radioactivity and OZ439 specific radioactivity versus time plot (in the same plot). A linear plot including SD bars, and a semi-logarithmic plot will be provided [treatment A, Part 1].
- Geometric mean oral OZ439 concentration vs time plot for treatments C and D in the same plot. A linear plot including SD bars, and a semi-logarithmic plot will be provided [Part 2].
- Geometric mean oral OZ439 concentration vs time plot for treatments A, B and C (with C dose-normalized to 800mg) in the same plot. A linear plot including SD bars, and a semi-logarithmic plot will be provided [Part 1 and 2].
- Mean plot of oral cobicistat concentration vs time (linear) [treatment D, Part 2].

Linear and semi-logarithmic plots of the combined individual plasma concentration by actual sampling time will be provided in a single plot by treatment and analyte (total radioactivity, OZ439, [C]-OZ439 and cobicistat).

Linear and semi-logarithmic plots of the individual plasma concentration by actual sampling time will be provided by subject (1 subject per page). For Part 1, total radioactivity, OZ439 and [C]-OZ439 concentration-time profiles will be shown in the same plot; For Part 2, OZ439 concentration-time profiles for Treatments B, C and D will be shown in the same plot. The cobicistat concentration-time profiles (Part 2, Treatment D only) will be presented separately. In all plots, colours will be used to distinguish between treatments.

All individual subject plasma concentration data will be listed.

### 16.3 Pharmacokinetic Parameters

PK parameters for total radioactivity, OZ439 and cobicistat will be estimated using non-compartmental methods with Phoenix WinNonlin® Version 6.3.

The plasma PK parameters will be estimated from the concentration-time profiles for all subjects in the safety population. In estimating the PK parameters, BQL values at the beginning of the profile will be set to zero. BQL values that occur after the first quantifiable point will be considered missing. Values that are embedded between BQLs, or quantifiable values occurring after 2 or more BQLs, will be set to missing at the discretion of the pharmacokineticist.

Actual blood sampling times will be used in the PK parameter calculations. If the actual time or dose time is missing, the scheduled time may be substituted in order to calculate the PK parameter.

The terminal elimination rate constant ( $\lambda_z$ ) will be determined by plotting the concentration data versus time on a semi-logarithmic scale. The time interval of the terminal elimination phase will be determined by visual inspection. Linear regression on log-transformed concentrations within this interval will be used to calculate the terminal elimination rate constant. At least 3 data points are required to obtain a reliable  $\lambda_z$  and associated parameters. Points prior to and including  $C_{max}$  will not be used to estimate  $\lambda_z$ . Terminal half-life and  $\lambda_z$  values (and derived parameters) will be flagged if  $\lambda_z$  cannot be accurately estimated (adjusted  $r^2 < 0.8$ ). In calculations of AUC parameters, the linear up / log down trapezoidal method will be used. For  $AUC_{0-inf}$ , if the %extrapolation from last quantifiable concentration to infinity  $>20\%$ , then the data will be flagged.

Descriptive statistics (number of subjects, mean, geometric mean, SD, CV%, median, minimum, and maximum) will be used to summarize the calculated PK parameters by treatment. For  $t_{max}$ , the geometric mean will not be presented.

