#### 5.1.1 Primary Endpoints

- Part 1: PK: absolute oral bioavailability ( $F_{po}$ ) of OZ439
- Part 2: PK of OZ439:  $C_{max}$ ,  $C_{168h}$ ,  $AUC_{0-168h}$  and  $AUC_{0-inf}$

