## 6.1 Sample Size Considerations

The study is exploratory and no formal sample size calculation has been made. Based on experience from previous similar studies and taking into account OZ439 large variability, a total of 8 subjects enrolled in Part 1 of the study to achieve a minimum of 6 evaluable subjects is considered sufficient. A total of 8 subjects is also considered sufficient to assess the effects of the total dosing volume and of dose to volume ratio on OZ439 PK under fasted conditions (in combination with Part 2). In Part 2 of the study a sample size of 18 subjects is considered appropriate to estimate the increase in OZ439 exposure in the

presence of a single dose of 150 mg cobicistat with sufficient precision, assuming a mean ratio of 2. Based on the assumptions of a point estimate (mean ratio) of 2.0 and a CV of 23%, a sample size of 18 subjects would give a 90% confidence interval (CI) of 1.75 - 2.28 and this number of subjects is therefore considered sufficient. In Part 2, 18 subjects will be randomized to ensure data in 15 evaluable subjects for the PK endpoints. A subject will be considered evaluable for the primary analysis if they have sufficient PK data to estimate the primary endpoints  $C_{max}$  and  $AUC_{0-inf}$  for the 3 treatments. Note: the primary analysis refers to the statistical analysis of the treatment comparisons defined in Section 16.3.1.

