## 7.0 Overview of Planned Analysis

### 7.1 Changes from Protocol

In the protocol it was stated that a subject will be considered evaluable for the primary analysis if they have sufficient PK data to estimate all of the primary endpoints ( $C_{max}$ ,  $C_{168h}$ ,  $AUC_{0-168h}$ , and  $AUC_{0-inf}$ ) for the 3 treatments. This was changed in the SAP to: 'a subject will be considered evaluable for the primary analysis if they have sufficient PK data to estimate the primary endpoints  $C_{max}$  and  $AUC_{0-inf}$  for the 3 treatments'.

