#### 9.1.2 Imputation

Unless otherwise noted data will not be imputed. Exceptions are missing start and end times of AEs, see Section 17.1.1 and PK concentrations under lower limit of quantification (LLOQ), see Section 16.2.

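### Read literally, the SAP deletes a below-LLOQ 168 h sample from the C168h analysis (a Part 2 primary endpoint); if such values occur mainly in Treatment C, D/C moves toward 1 and dose-normalised B/C moves down

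*SAP*

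**What the plan says.** - SAP 5.1.1, under "Part 2: PK of OZ439", lists C168h with Cmax, AUC0-168h and AUC0-inf as primary endpoints. Section 16.1 includes it in the PK parameter table as "Observed plasma concentration at 168 hours post-dose" and leaves its programming note empty.
- Section 16.3, on estimating PK parameters, sets BQL values at the start of a profile to zero. For later ones, "BQL values that occur after the first quantifiable point will be considered missing".
- Section 16.2 states that BQL plasma concentrations "will be set to ½ LLOQ in the computation of mean concentration values". Section 9.1.2 rules out imputation in general and names as one exception "PK concentrations under lower limit of quantification (LLOQ), see Section 16.2".
- Section 7.1 records that the protocol's definition of an evaluable subject required "sufficient PK data to estimate all of the primary endpoints", and that the SAP now requires only Cmax and AUC0-inf. Section 10.4 carries the narrowed definition: "a subject will be considered evaluable for the primary statistical analysis if they have sufficient PK data to estimate the primary endpoints". Only two parameters are named there, Cmax and AUC0-inf, and both are needed under every Part 2 treatment.
- Section 16.3.2 analyses log C168h in a mixed model with treatment, period and sequence as fixed effects and subject within sequence as random. The ratios D/C and B/C come from it, with C dose-normalised to 800 mg for B/C.
- The only planning figures are in Section 6.1: "Based on the assumptions of a point estimate (mean ratio) of 2.0 and a CV of 23" per cent, for the increase in OZ439 exposure with cobicistat.

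**The concern.** Treating late BQL values as missing is ordinary practice for AUC and λz, which use the whole profile. C168h is a single observed late concentration. A BQL result there says that the value is low, so calling it missing discards information and does so selectively.

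The narrowed evaluability rule means that a subject with a BQL 168 h sample can stay in the analysis. Samples at 24, 48, 72 and 96 h can still support λz and AUC0-inf. Only the low C168h value leaves; the subject's other periods remain. If C has the lowest un-normalised concentrations, the deleted values come mostly from C, its mean rises, and both ratios with C in the denominator fall. The mixed model does not repair this, because the chance of being missing depends on the unobserved value itself.

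At stake are the estimated cobicistat effect on one of four primary parameters and the exploratory B/C comparison for the same parameter.

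**Working it through.** **1. The plan's own figure.** Inputs from Section 6.1: ratio 2.0, CV 23%, n = 18, 90% CI. The log-scale within-subject SD is √ln(1 + 0.23²) = 0.227. The standard error of a treatment difference is 0.227 × √(2/18) = 0.0757. With 16 df, t = 1.746, so the half-width is 1.746 × 0.0757 = 0.132. The interval is 2.0 × exp(±0.132) = 1.75 to 2.28, which reproduces the SAP.

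**2. Which rule covers C168h.**

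| Section | Scope stated | BQL handling | Covers C168h in the ANOVA? |
|---|---|---|---|
| 16.3 | Estimating PK parameters | Missing after first quantifiable value | Yes, on its words |
| 16.2 | Mean concentration values | ½ LLOQ | Not on its words |
| 9.1.2 | Pointer to 16.2 | As 16.2 | Only by extending 16.2 |

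The literal reading is deletion. The alternative is possible but less well supported.

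**3. Effect of deletion.** Simulation of the Part 2 design: 18 subjects, six sequences, log-normal C168h, REML fit of the Section 16.3.2 model, 400 trials per scenario. Taken from the SAP: n, sequences, model, CV 23%, D/C = 2.0. Assumed: that these two planning figures apply to C168h; a true dose-normalised B/C of 1.0 (un-normalised B twice C); the between-subject CV; a within-subject CV of 50% as the alternative; and an LLOQ set to give the stated BQL share in C. Fits to the complete data returned D/C 1.99-2.01 and B/C 0.99-1.00 in the scenarios shown.

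| Within CV | Between CV | BQL in C | Deletion: D/C | Deletion: B/C | ½ LLOQ: D/C | ½ LLOQ: B/C |
|---|---|---|---|---|---|---|
| 23% | 40% | 10% | 1.95 | 0.97 | 2.09 | 1.05 |
| 23% | 40% | 30% | 1.85 | 0.93 | 2.24 | 1.13 |
| 23% | 80% | 10% | 1.96 | 0.98 | 2.05 | 1.03 |
| 23% | 80% | 30% | 1.91 | 0.95 | 2.09 | 1.04 |
| 50% | 40% | 10% | 1.84 | 0.92 | 2.09 | 1.04 |
| 50% | 40% | 30% | 1.67 | 0.83 | 2.15 | 1.07 |
| 50% | 80% | 10% | 1.89 | 0.95 | 2.04 | 1.02 |
| 50% | 80% | 30% | 1.76 | 0.87 | 2.06 | 1.02 |

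At within-subject CV 23% with about 30% of C values BQL, only 2-8% of B and D values are BQL, which is what drives the shift. A second simulation (600 trials per scenario) at 5% BQL, about 1 of 18, gave D/C 1.97-1.98 and B/C 0.985-0.990 for within-subject CV 23% and between-subject CV 50-80%.

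**4. Size.** At within-subject CV 23%, D/C falls by 1 − 1.98/2 = 1% to 1 − 1.95/2 = 2.5% at 5-10% BQL, and by 1 − 1.91/2 = 4.5% to 1 − 1.85/2 = 7.5% at 30%. The log shifts are ln(2/1.95) = 0.025 and ln(2/1.85) = 0.078, against the planned half-width of 0.132.

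**5. When nothing happens.** With no BQL value at 168 h, neither ratio moves. With a true D/C of 1.0, D/C stayed at 0.99-1.01 in all 24 scenarios run, because C and D then lose values equally. B/C still fell, to 0.92-0.97 at 20-30% BQL and within-subject CV 23%.

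**6. The two simple rules do not bracket the truth.** At within-subject CV 50%, between-subject CV 80% and 50% BQL, deletion gives D/C 1.60 and ½ LLOQ gives 1.92, both below 2.0.

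**7. Left-censored likelihood.** In 320 fits (40 in each of 8 scenarios) the mean estimates were D/C 1.99-2.01 and B/C 0.99-1.01, and no fit failed. Interval coverage was not examined.

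**The case against.** The bias needs two things that the SAP does not establish: the deletion reading, and BQL values at 168 h. No LLOQ or BQL rate is given. Appendix 3 samples Treatment D to 312 h, which hints that OZ439 is usually measurable at 168 h, although C is sampled only to 168 h. This stands, and it limits the severity.

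The reading can be contested. C168h is an observed concentration with no WinNonlin note, and 9.1.2 sends BQL concentrations to 16.2. That is fair, but 16.2 limits itself to mean values. If the second reading is accepted, the SAP supports two rules for one primary endpoint, and in the table above they err in opposite directions.

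Readers would have a partial cross-check. Section 16.2 calls for geometric means at each time with ½ LLOQ (unless over half the values are BQL), and all individual concentrations are listed. The loss would therefore be visible, but the ANOVA ratio would be uncorrected.

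The ratio of 2.0 and CV of 23% are stated for OZ439 exposure, not for C168h, and the SAP assumes no B/C ratio. This stands: the B/C figures rest on assumed dose proportionality. At 5-10% BQL and CV 23% the effect is also small. A log shift of 0.025 lowers the coverage of a nominal 90% interval only to about 88% (noncentral t, 32 df).

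The censored model was checked for point estimates only. Maximum likelihood with normal limits would itself give about 87% coverage here even without censoring (residual variance divided by 36 instead of 32 df), so small-sample intervals are needed.

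A reader might infer that the SAP's cobicistat result for C168h will be biased, or materially so. The document does not support that, since occurrence and size both depend on unstated quantities.

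**Conclusion.** The point holds conditionally and is minor. On its literal wording, the only BQL rule for PK parameters would remove low C168h values selectively, and a less literal reading gives a different answer. If BQL values occur at 168 h and un-normalised C168h is lower in C than in D and B, both ratios are understated by about 1-3% at 5-10% BQL in C and roughly 5-8% at 30%. These sizes assume a within-subject CV of 23%, a between-subject CV of 40-80%, a true D/C of 2.0 and a true dose-normalised B/C of 1.0. At these values D/C stays inside the planned interval of 1.75-2.28. At a within-subject CV of 50%, which is not an SAP figure, 30% BQL takes D/C to 1.67-1.76. Confidence is high on the direction and low on whether the situation arises at all.

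**What to change.** Amend Section 16.3 so that the missing rule applies to AUC, λz and parameters derived from them. State in Section 16.1 or 16.3 that a BQL C168h is a value below the LLOQ, not a missing one. Add to the C168h output the number of BQL values at 168 h by treatment.

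If none occur, run the planned ANOVA unchanged. If any occur, do not rely on deletion alone. Report a left-censored log-scale analysis with the same fixed effects and random subject, using t-based or otherwise small-sample-corrected intervals, beside the deletion and ½ LLOQ results. Do not describe those two as bounds.

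The cost is a few sentences of SAP text and a little code that runs only if needed. The censored fit could be unstable with 18 subjects; the side-by-side results give a fallback. Dosing, sampling and the other endpoints are unaffected.
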